9.4. Masking

Optometrists obtaining the primary outcome measure will be masked to treatment allocation. Masked assessors will not have access to clinical information about the participant and only to blank worksheets, which they will be given to record pertinent data. The trial statistician, who has no role in decision-making with regard to the conduct of the trial, will be unmasked. This will facilitate linkage with the DMEC. The remainder of the trial team at the NICTU will be unmasked for the purposes of managing data collection, reviewing cases to assess protocol deviations, and safety reporting. Staff delivering treatments and participants receiving the treatments will not be masked to treatment allocation.

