14. STATISTICAL CONSIDERATIONS

14.1. Sample Size

COMBAT is powered to demonstrate treatment equivalence for the primary outcome. Based on two one-sided t-tests at the 2.5% significance level, a 15.2-letter standard deviation (27) and an equivalence margin of +/- 7 ETDRS letters (with a difference of 7 or fewer letters being considered not clinically meaningful) (28,29), 248 participants would be required to be 90% sure the 95% confidence interval will exclude a difference in means of more than 7 ETDRS letters. Allowing for 10% dropout, we will require a minimum of 276 participants. This sample size will be sufficient to detect a difference of 16% in the rate of retinal reattachment surgery between groups, which is clinically relevant.

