14.2. Data Analysis

Statistical Methods

As this is an equivalence trial for the primary outcome, the primary statistical analysis will be per protocol, but an intention-to-treat analysis will be also undertaken (30). The difference between randomised groups for change in BCVA (using 95% confidence interval [CI]) from baseline to week 52 post surgery) will be compared to the permitted maximum difference (PMD) of +/-7 ETDRS letters using an analysis of covariance model adjusting for baseline BCVA and minimisation factors. If the 95% CI of the treatment difference lies wholly within both upper and lower margins of the PMD, phacovitrectomy could be deemed equivalent to vitrectomy alone. A 7 ETDRS letter equivalence margin is not considered clinically important and could relate to test re-test variability (28,29).

A secondary analysis from baseline to week 52 post-surgery will be compared to the permitted maximum difference (PMD) of +/-7 ETDRS letters using two one sided 2-sample t-tests.

The primary analysis will use data from the study eye only. Analyses of categorical secondary outcomes will use general linear models (GLM) with adjustment for minimisation covariates. Relative risk, risk difference and odds ratio will be reported where possible. Analyses of continuous secondary outcomes will use ANCOVA adjusting for corresponding baseline and minimisation factors, as appropriate. For time to best vision, we will use two-sample t-test or non-parametric alternative based on distribution of the data. For change in BCVA over time, we will compare the Area Under the Curve between groups. Statistical significance for secondary outcomes will be based on two-sided tests with p<0.05 as the criterion for statistical significance.

The primary outcome will be analysed according to pre-specified subgroups (e.g. surgeon experience [consultant/vitreoretinal fellow]; macula/fovea on/off, presence of PVR-C; number of quadrants of detached retina, presence of inferior breaks in detached retina) by including the corresponding interaction term in the GLM and using 99% confidence intervals.

A sensitivity analyses will be conducted for the primary outcome; looking at change in vision, if surgery takes place more than 3 days after the baseline assessment.

Baseline characteristics, follow-up measurements (including occurrence of cataract surgery) and safety data will be reported using descriptive summary measures depending on scale of measure/distribution.

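### Equivalence is decided on the per-protocol set, with no stated role for the planned intention-to-treat analysis, and the sample size allows only for dropout

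*Protocol*

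**What the plan says.** Protocol section 14.2 (Statistical Methods) justifies the choice of analysis set by the equivalence design: "the primary statistical analysis will be per protocol, but an intention-to-treat analysis will be also undertaken". The primary comparison is an analysis of covariance of change in BCVA at week 52, adjusted for baseline BCVA and the minimisation factors. One decision criterion follows: phacovitrectomy may be deemed equivalent if the 95% interval for the difference lies wholly within ±7 letters. The text does not say what follows if the two analysis sets disagree.

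Section 14.1 gives the sample size. "Based on two one-sided t-tests at the 2.5% significance level", with a standard deviation of 15.2 letters and "an equivalence margin of +/- 7 ETDRS letters", it concludes that "248 participants would be required to be 90% sure the 95% confidence interval will exclude a difference in means of more than 7 ETDRS letters". The only inflation is this: "Allowing for 10% dropout, we will require a minimum of 276 participants".

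Section 14.2 (Missing Data) bases the principal analysis on available cases without imputation. Under section 9.4 the optometrists who measure the primary outcome are masked, while surgeons and participants are not. The rest of the trials unit team "will be unmasked for the purposes of managing data collection, reviewing cases to assess protocol deviations, and safety reporting".

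**The concern.** A per-protocol set is selected after randomisation. In this trial the allocation is known to the surgeon and the participant, and the protocol itself gives reasons to expect some departures from it. Section 8.1 says that most UK vitreoretinal surgeons do not currently do the combined operation for retinal detachment, and section 11.1 allows fellows to operate. If the eyes that depart from allocation also see worse, leaving them out removes poor results, possibly by different routes in the two arms. The per-protocol difference could then move towards or away from zero.

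Intention-to-treat is not a safe sole basis for equivalence either, because departures from allocation tend to make the arms look alike. The two analyses fail in different ways, which is the reason for asking them to agree. The protocol plans both but lets one decide. What is at stake is the trial's main conclusion: a claim of equivalence could stand on the selected set when the randomised comparison does not support it.

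The second matter is consistency. The 90% power refers to 248 analysed participants, the stated primary set is per protocol, and the inflation covers only dropout.

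**Working it through.** **Inputs from section 14.1:** standard deviation 15.2; margin 7; two one-sided tests at 2.5%; power 90%; 10% dropout. Section 9.1 gives 1:1 allocation. The true difference is not stated. Zero is assumed, and it reproduces the plan's figure.

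**1. Reproducing 248 and 276.** With a true difference of 0, each one-sided test needs power 1 − 0.10/2 = 0.95. By the normal approximation,

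n per arm = 2 × [15.2 × (1.960 + 1.645) / 7]² = 122.5, so 123 per arm, or 246 in total.

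Exact t-based power for the pair of tests is 89.8% at 246 and 90.1% at 248, so 248 is the smallest even total that reaches 90%. Then 248 / 0.9 = 275.6, rounded up to 276. Both figures are right.

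**2. Slack for per-protocol exclusions.** 276 × 0.9 = 248.4, against 248 needed. There is none.

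**3. Unadjusted power if a share e of completers is also excluded.** The analysed number is 276 × 0.9 × (1 − e). The protocol gives no value for e, so a range is shown.

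| e (assumed) | analysed | power | randomised for 248 per protocol: 248 / [0.9 × (1 − e)] |
|---|---|---|---|
| 0% | 248.4 | 90.2% | 276 |
| 2% | 243.4 | 89.4% | 282 |
| 5% | 236.0 | 88.2% | 291 |
| 10% | 223.6 | 85.8% | 307 |
| 20% | 198.7 | 79.6% | 345 |

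**4. Effect of the planned covariance adjustment.** If 15.2 is an unadjusted standard deviation and the covariates correlate r with the outcome (both assumptions), the residual standard deviation is 15.2 × √(1 − r²). At 10% exclusions, power is then 87.6% for r = 0.2, 89.8% for r = 0.3 and 92.5% for r = 0.4.

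**5. Cost of requiring both sets to agree.** This was simulated with 124 completers per arm, no true difference and random exclusions in both arms (200,000 trials for each rate).

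| excluded per arm | per protocol alone | both sets | cost |
|---|---|---|---|
| 6 of 124 (5%) | 88.2% | 87.1% | 1.1 points |
| 12 of 124 (10%) | 86.0% | 84.6% | 1.4 points |

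**6. How far informative exclusion could matter (illustration only).** Suppose the true difference is exactly 7 letters, so that a declaration of equivalence is wrong 2.5% of the time. Suppose too that exclusions occur only in the worse arm, in eyes that do 20 letters worse than that arm's average. The arm's mean moves by about e × 20. The chance of wrongly declaring equivalence per protocol becomes:

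- e = 2% (0.4 letters): 4.0%
- e = 5% (1.0 letter): 7.3%
- e = 8% (1.6 letters): 12.5%

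If those eyes do 10 letters worse, the figures are 3.2%, 4.4% and 6.0%. The protocol gives neither the rate nor the deficit.

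**The case against.** Per protocol as the primary analysis of an equivalence trial is a deliberate and referenced choice, and an intention-to-treat analysis is planned beside it. The wording of the criterion is permissive, and section 14.2 promises a detailed public SAP, where a rule for discordant results could sit. This stands in part. It would be wrong to say that intention-to-treat is absent. But the protocol itself names the deciding set and the criterion, so the gap lies in what it states.

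A reader might infer from section 9.4 that unmasked staff will choose who enters the per-protocol set. The document does not say so. It lists review of deviations among the tasks of trial conduct, and checking that the allocated operation was done requires knowing the allocation. Who settles membership of the set, and when, is ordinary SAP matter.

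A reader might also infer that particular surgical events will lead to exclusion. No section says so, and some may be on protocol: section 8.2 has complications treated as in standard practice, and cataract surgery when a cataract develops is part of the comparator. Exclusions in both arms could also partly offset each other. The one-arm illustration is therefore a scenario, not a forecast.

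Finally, a reader might conclude that the trial is under-powered. That is not shown. The stated figures reproduce, 276 is described as a minimum, the loss is under 2 points from the nominal 90% at 5% exclusions, and the covariance adjustment may recover it.

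**Conclusion.** The point holds on the decision rule. The protocol lets the per-protocol interval alone settle equivalence and says nothing about a conflicting intention-to-treat result. The size of any bias cannot be known from the document. Under the assumed one-arm scenarios above, the risk of a false claim rises from 2.5% to between 3.2% and 12.5%.

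On sample size only a narrow point stands. The 248 and 276 are correct, but the 10% is described as dropout and uses up all the slack, so the 90% makes no separate allowance for exclusions from the stated primary set. Unadjusted power is about 88% at 5% and 86% at 10% of completers excluded, assuming no true difference. By itself this would be minor, and it disappears if the 10% was meant to cover exclusions as well.

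**What to change.** - **Section 14.2:** state that equivalence will be concluded only if the 95% interval lies within ±7 letters in both the per-protocol and the intention-to-treat analyses. The cost is about 1 point of power at 5–10% random exclusions.
- **Section 14.1:** state that the 90% applies to 248 participants in the per-protocol set. Then either say that the 10% covers per-protocol exclusions as well as dropout, or restate unadjusted power as about 88% with 5% and 86% with 10% of completers excluded, noting that these rates are assumed and that covariate adjustment may offset the loss. The stated power may then look less favourable.

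Both are wording changes and need no added visits, data or participants. Fixing per-protocol status before database lock, by reviewers who have not seen post-operative BCVA, is a sensible item for the SAP. Its absence from the protocol is not an error.

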9. ASSIGNMENT OF TREATMENT

9.1. Sequence Generation

When a potentially eligible person with a RRD is identified, they will be informed about the COMBAT study. If they are willing to take part, informed consent will be obtained, and eligibility confirmed. If eligible, the baseline visit (see Data Collection section, below) will be undertaken (as soon as possible and before the surgery) and participants will be randomised (1:1) to receive phacovitrectomy or vitrectomy. An automated system with the allocation concealed to the ophthalmologist recruiting the participant will be used to generate the random allocation sequence. A minimisation algorithm will be used to ensure balanced allocation of participants across treatment groups for potentially important factors including centre, surgeon's experience (consultant/vitreoretinal fellow), presenting BCVA (BCVA \geq 69 ETDRS letters [Snellen equivalent \geq 20/40; logMAR \geq 0.3], 24–68 ETDRS letters [Snellen equivalent \leq 20/50-20/320; logMAR 0.4–1.2], \leq 24 ETDRS letters [Snellen equivalent \leq 20/320]); macular status (macula on & fovea on, macula off & fovea on, fovea off \leq 7 days, fovea off 7-14 days, fovea off 15-30 days, fovea off \leq 30 days); and presence/absence of PVR-C.

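### The supporting equivalence test and the time-to-best-vision comparison are specified without adjustment for the minimisation factors, which makes them needlessly conservative

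*Protocol*

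**What the plan says.** Section 9.1: "A minimisation algorithm will be used to ensure balanced allocation of participants across treatment groups for potentially important factors". The factors listed are centre, surgeon experience (consultant or fellow), presenting BCVA in three bands, macular status in six levels, and PVR-C.

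Section 14.2 sets the primary comparison of change in BCVA as an ANCOVA that includes baseline BCVA and the minimisation factors, with equivalence judged from its 95% confidence interval. Adjusted ANCOVA is also the general rule for continuous secondary outcomes, with room left for exceptions. Two analyses are then named in unadjusted form:

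- The supporting equivalence analysis, in which the baseline-to-week-52 comparison "will be compared to the permitted maximum difference (PMD) of +/-7 ETDRS letters using two one sided 2-sample t-tests".
- A secondary outcome: "For time to best vision, we will use two-sample t-test or non-parametric alternative", the choice depending on the distribution of the data.

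Section 14.1 sizes the trial on two one-sided t-tests at 2.5% each, with an SD of 15.2 letters and "an equivalence margin of +/- 7 ETDRS letters". It concludes that "248 participants would be required to be 90% sure the 95% confidence interval will exclude a difference in means of more than 7 ETDRS letters".

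**The concern.** Balancing the arms on prognostic factors makes the true sampling variance of the between-arm difference smaller than under simple randomisation. A two-sample t-test estimates its standard error from the total within-arm spread, which still contains the variation due to those factors. The stated error rates are then not the ones the test delivers: the interval is wider than 95% coverage requires, and the test is less sensitive than one that uses the design. The same holds for a two-sample comparison of time to best vision, to the extent that the factors predict that outcome.

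At stake is a supporting equivalence test that could miss the margin when the primary ANCOVA meets it, simply because it leaves out information already collected, and a secondary comparison that may give up precision for nothing.

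**Working it through.** **Inputs.** From Section 14.1: margin Δ = 7 letters, σ = 15.2 letters, 2.5% per one-sided test, 248 evaluable, so n = 124 per arm, and 10% dropout. Assumed: true difference 0 (not stated, but it reproduces the plan's number); R², the share of outcome variance explained by the balanced factors, from 0 to 0.5 (no figure in the protocol); and perfect balance on those factors.

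**1. The plan's own figure.** The normal approximation at zero difference, with 95% power per side, gives n = 2(1.960 + 1.645)² × 15.2² / 7² = 122.6, so 123 per arm. The exact t-based calculation gives power of 89.84% at 123 per arm and 90.15% at 124 per arm, hence 248. Dropout: 248 / 0.90 = 275.6, so 276. Both figures reproduce, and they reproduce for an *unadjusted* two-sample test with SD 15.2.

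**2. Standard error of the unadjusted test.** SE = 15.2 × √(2/124) = 15.2 × 0.1270 = 1.930. With t(246 df) = 1.970, the half-width is 1.970 × 1.930 = 3.80 letters, whatever R² is.

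**3. What balance does.** With the factors balanced, the true standard error is 1.930 × √(1 − R²), so the t-test's standard error is too large by a factor 1/√(1 − R²). Coverage of the nominal 95% interval is approximately 2Φ(1.970/√(1 − R²)) − 1. At R² = 0.1 this is 2Φ(2.077) − 1 = 96.2%. At R² = 0.5 it is 2Φ(2.786) − 1 = 99.5%. Simulation (100,000 draws per row, total SD fixed at 15.2) agrees:

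| R² | Adjusted SD | Coverage, unadjusted 95% CI | One-sided error at the margin (nominal 2.5%) | Power, unadjusted | Power, ANCOVA |
|---|---|---|---|---|---|
| 0 | 15.20 | 95.0% | 2.6% | 90.3% | 90.1% |
| 0.1 | 14.42 | 96.3% | 2.0% | 92.0% | 93.5% |
| 0.2 | 13.60 | 97.2% | 1.4% | 93.5% | 96.2% |
| 0.3 | 12.72 | 98.1% | 1.0% | 95.2% | 98.2% |
| 0.4 | 11.77 | 98.9% | 0.6% | 96.7% | 99.3% |
| 0.5 | 10.75 | 99.4% | 0.3% | 98.0% | 99.8% |

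The ANCOVA column is the exact t-based power at the adjusted SD with two-sample degrees of freedom, so it slightly overstates power once many centres are fitted. In the R² = 0 row the two tests are the same, and the small differences are simulation error.

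**4. Reading the table.** The unadjusted interval over-covers and the error rate at the margin falls below 2.5%. The power gap to the ANCOVA is 93.5 − 92.0 = 1.5 points at R² = 0.1 and 98.2 − 95.2 = 3.0 points at R² = 0.3. In no row does the unadjusted test fall below the planned 90%.

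**5. Time to best vision.** Section 12.4 defines it as the earliest time point at which the best BCVA is recorded. With masked BCVA scheduled at weeks 6, 12 and 52, it takes essentially three values. The mechanism in step 3 applies, but the protocol gives nothing from which to set R² for this outcome, so no size is given.

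**The case against.** **An unadjusted supporting analysis is a legitimate choice.** It is labelled secondary, the equivalence criterion is attached to the ANCOVA interval, and an over-wide interval cannot create false equivalence. This largely stands and limits the weight of the point. What remains is that the test is not described as a deliberately unadjusted sensitivity analysis, and its nominal error rates are not its actual ones.

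**Baseline is not ignored altogether.** The supporting test runs from baseline to week 52, which reads as a change score. That is right: baseline is subtracted. It is not used as a covariate, and the other minimisation factors do not enter.

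**Three stronger readings are tempting, and the document does not support them.**

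- A reader might infer that the supporting test lacks the 90% power of Section 14.1. That figure was computed for this kind of test and reproduces. Power falls below 90% only if 15.2 is already a baseline-adjusted residual SD: with balanced factors, to about 88%, 85%, 80% and 60% at R² of 0.1, 0.2, 0.3 and 0.5. Section 14.1 does not say that it is. The wide span of presenting BCVA may make one wonder, but the protocol gives no BCVA distribution from which to settle it.
- A reader might conclude that Section 14.1 should declare 15.2 a residual SD. Without the source, that could insert a false statement.
- A reader might add change in BCVA over time, where the text says only "we will compare the Area Under the Curve between groups". That names a summary measure and does not exclude adjustment. The general ANCOVA rule may cover it, and the detail can sit in the SAP.

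**Baseline may not predict which visit gives the best vision.** This is fair, and it is why no size is claimed for that outcome.

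**Conclusion.** The point holds as a minor one. Two analyses named in Section 14.2 leave out the factors on which allocation is balanced, although the primary model and the general rule for continuous secondary outcomes use them. For the supporting equivalence test, the standard error is too large by a factor of 1.05 to 1.41 (1/√0.9 to 1/√0.5). These sizes rest on the assumed R² range, a true difference of zero, 15.2 as the raw SD of change, and perfect balance. Minimisation achieves balance only approximately, so actual coverage would lie between 95% and the tabulated value. For time to best vision the direction is clear if the factors are prognostic, but the size is unknown. The error is conservative in both cases, and neither the primary ANCOVA conclusion nor the sample size is affected.

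**What to change.** In Section 14.2:

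1. Take the two one-sided tests from the primary ANCOVA, with baseline BCVA and the minimisation factors. Alternatively, delete the supporting analysis: an ANCOVA 95% interval lying inside ±7 letters is already two one-sided tests at 2.5%, so nothing is lost.
2. Adjust the time-to-best-vision comparison for the minimisation factors and baseline BCVA. If a non-parametric route is kept, use a form that can carry these factors, such as a stratified rank test or an ordinal model.

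The cost is a few words in the protocol, repeated in the SAP. The covariates are all recorded by the time of randomisation, and no further participants, visits or data are needed.

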12.4. Clinical Outcomes

Best-Corrected Visual Acuity (BCVA)

The primary outcome is change in BCVA from baseline to 52 weeks (+/- 6 weeks) after surgery in the study eye. There is no consensus on the core outcomes to be measured in trials for RRD but BCVA is routinely measured in the standard care of patients with RRD and in ophthalmology trials. It is considered, together with retinal reattachment, as a main outcome of surgical success in clinical practice. BCVA closely relates to patient-reported quality of life. Full-refracted distance BCVA will be measured in both eyes using the ETDRS Visual Acuity charts at 4 meters by masked optometrists/ophthalmologists at baseline and at week 6, 12 and 52 after surgery, following the COMBAT SOP.

Note: If the surgery takes place more than three days after the baseline assessment, or if the patient reports a change in their vision since the baseline assessment, the BCVA should be repeated before the surgery.

Retinal Reattachment

Patients will be evaluated using slit-lamp biomicroscopy with wide angle non-contact or contact lenses and/or indirect ophthalmoscopy, as per standard practice at participating sites, and the status of the retina (fully attached/detached) will be recorded in the appropriate CRF.

Intraoperative and Postoperative Complications

Intra- and post-operative complications will be prospectively recorded using CORDS (The Classification for the Reporting of Complications in Retinal Detachment Surgical Trials) (19), a robustly developed classification of complications of vitreoretinal surgery (18). Complications will be scored as per this classification and analysed. Intraoperative and postoperative complications of cataract surgery will be also recorded.

Furthermore, presence/absence of posterior capsule opacification (PCO) and performance of YAG laser posterior capsulotomy will be prospectively recorded during the trial in the appropriate CRF (Note: surgeons who routinely do posterior capsulectomy at the time of the phacovitrectomy will be allowed to do so in COMBAT, recording this procedure in the pertinent surgical CRF).

Number and Type of Surgeries Performed

The number and type (e.g. surgery for retinal re-detachment – i.e. if surgical failure occurs; cataract surgery; other) of surgeries performed throughout the trial will be recorded in the appropriate CRFs.

Refractive Error

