12.5. Patient Reported Outcomes and Health Economics Study Instruments

EuroQol-5 Dimension-5 Level (EQ-5D-5L)

The EQ-5D-5L (20) is a generic preference-based measure of health, which provides a description of health using five dimensions (mobility, self-care, usual activities, pain and discomfort, and anxiety and depression), each with five levels of severity. Responses can be converted to an overall utility score and used to calculate quality adjusted life years (QALYs). Respondents are also asked to place their health on a visual analogue scale where 0 represents the worst imaginable health state and 100 the best imaginable health state.

National Eye Institute Visual Function Questionnaire (NEI VFQ-25)

The National Eye Institute Visual Function Questionnaire (NEI VFQ-25) will be used to provide vision specific patient-reported quality of life (QoL) (21). The NEI VFQ-25 is a validated questionnaire that has been used widely to evaluate visual outcomes in patients with eye diseases including RRD. In addition to eliciting information about general health and vision, it specifically addresses difficulty with near vision, distance vision, driving and the effect of light conditions on vision.

The above tools will provide a comprehensive evaluation of health-related and vision-related quality of life at baseline, and at 6, 12 and 53 weeks post-surgery. This will allow examination of a potential "response shift" that may occur over time. Response shift occurs when an individual reports their QoL

at two (or more) points in time but does not use the same frame of reference on each occasion, thereby distorting the comparison of QoL over time. Questionnaires will be self-completed by participants with large font questionnaires used when required.

In addition to the standard 25 questions contained in the NEI VFQ-25 questionnaire, we will include a question aimed at assessing the perceived change in QoL by the participants from preoperative levels. This question will be added at each time point this questionnaire is administered, except at the baseline visit. We will be asking participants how much they perceive their QoL to have changed since before they had their surgery [with potential answers being "much better", "slightly better", "about the same", "slightly worse", "much worse"]. Answers to this question would allow anchoring QoL data with visual outcomes data.

ModRUM (Modular Resource Use Measure)

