Quality of life will be assessed at baseline and at different time points throughout the trial. We will investigate the impact and nature of response shift (changes in quality-of-life assessment due to changes in an individual's frame of reference rather than 'true change'). The nature of response shift (reconceptualization, reprioritization, and recalibration) will be examined using Oort's procedure (31,32). Response shift will be determined by examining changes in the model parameters over time: the value of error variances and intercepts for recalibration; factor loadings for reprioritization; and pattern of factor loadings for reconceptualization. A sample size of 200 is likely to achieve 80-90% power in the assessment of response shift using SEM (32). Thus, the sample size of COMBAT (276 participants) should be adequate to address this. Oort's Procedure involves four major steps: 1) Establish an appropriate measurement model of observed scores at two times of measurement; 2) Construct a model verifying the hypothesis of no response shift and compare its fit with the model from step 1 using the likelihood ratio test (LRT) to determine the global presence of response shift. 3) If there is evidence of response shift, conduct an iterative process (by relaxing one constraint at a time) starting from the model in step 2. Relaxing the constraints on error variances (non-uniform recalibration) will be performed first, followed by intercepts (uniform recalibration) and factor loadings (reprioritization), thus following a hierarchy in testing the different forms of response shift proposed in previous research. This will continue until relaxing a proposed constraint leads to a non-significant LRT. 4) Estimate a final model, in which differences in factor means are indicative of "true change" after accounting for response shift. SEM models will be fitted using a robust maximum-likelihood estimator with a Satorra-Bentler correction. A root-mean-square error of approximation (RMSEA) close to 0.05 and comparative fit index (CFI) of 0.95 will be used as indicators of good fit. The LRT will be considered significant if the p-value is <0.05.

Health Economics Evaluation

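### The NEI VFQ-25 model could also adjust for baseline fellow-eye BCVA, which is already measured; the planned ANCOVA is valid but may be less precise than it could be

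*Protocol*

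**What the plan says.** - **Model.** Protocol section 14.2 (Statistical Methods): "Analyses of continuous secondary outcomes will use ANCOVA adjusting for corresponding baseline and minimisation factors, as appropriate". Secondary outcomes are tested two-sided at p<0.05.
- **Minimisation factors.** Section 9.1 lists "potentially important factors including centre, surgeon's experience (consultant/vitreoretinal fellow), presenting BCVA", followed by macular status and presence of PVR-C. No fellow-eye term appears.
- **Data collected.** Section 12.4: "Full-refracted distance BCVA will be measured in both eyes using the ETDRS Visual Acuity charts at 4 meters by masked optometrists/ophthalmologists at baseline". The same measurement is repeated at weeks 6, 12 and 52.
- **What the questionnaires measure.** Section 12.5 says of the NEI VFQ-25 that "it specifically addresses difficulty with near vision, distance vision, driving and the effect of light conditions on vision". It describes the EQ-5D-5L as a generic measure "using five dimensions (mobility, self-care, usual activities, pain and discomfort, and anxiety and depression".
- **Baseline questionnaire.** Section 14.2: "Quality of life will be assessed at baseline and at different time points throughout the trial". The baseline score is therefore available for the ANCOVA.
- **Study eye.** Section 14.2: "The primary analysis will use data from the study eye only". This restriction is stated for the primary analysis only, so it does not rule out a fellow-eye covariate in a secondary model.

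**The concern.** Reading, seeing at a distance and driving are done with both eyes. The eligibility criteria in section 7.2 do not limit fellow-eye vision, and section 10.4 allows for a fellow eye with its own detachment, so fellow-eye vision can differ widely between participants. Section 12.4 itself says that BCVA is closely related to patient-reported quality of life.

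The baseline NEI VFQ-25 score carries part of this information. But it is taken during an acute detachment, and sections 12.5 and 14.2 anticipate response shift, meaning that participants may judge their quality of life against a different frame of reference later on. A measured letter score does not depend on that frame. Some variation due to the fellow eye may therefore remain in the residual.

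At stake is the precision of one secondary comparison. Section 5.2 asks whether phacovitrectomy is equivalent on vision but superior on other outcomes, and section 10.2 lists vision-specific quality of life among them. The protocol gives no power or precision figure for this comparison.

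**Working it through.** **1. The protocol's own figure, to fix the evaluable number.** Inputs from section 14.1: SD 15.2 letters, margin 7 letters, two one-sided tests at 2.5%, 90% power, true difference 0.

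Normal approximation: n per arm = 2 × [15.2 × (1.960 + 1.645) / 7]² = 122.5, so 123 per arm and 246 in total. With the t distribution, power is 0.898 at 246 and 0.901 at 248, so the stated 248 reproduces. Dropout: 248 / 0.9 = 275.6, which rounds up to 276. This figure concerns the primary outcome and is not in question; 248 is used below as the evaluable number.

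**2. Effect of one added covariate.** Let r be the partial correlation of baseline fellow-eye BCVA with the week-52 NEI VFQ-25 score, given the baseline score and the minimisation factors.

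- Ratio of CI widths, new to planned = √(1 − r²).
- Allowing for the lost degree of freedom and chance imbalance, multiply by √(1 + 1/(df − 1)). With five covariate parameters already in the model, df = 248 − 2 − 5 − 1 = 240 and the factor is √(1 + 1/239) = 1.0021. The change in the t quantile is negligible. With 15 or 40 parameters (many centres), no result moves by more than 0.05 percentage points.
- Equivalent evaluable number = 248 / (1 − r²).

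| r (assumed) | CI narrower, 1 − √(1 − r²) | CI narrower, corrected | Equivalent evaluable number |
|---|---|---|---|
| 0 | 0% | −0.2% (wider) | 248 |
| 0.1 | 0.5% | 0.3% | 251 |
| 0.2 | 2.0% | 1.8% | 258 |
| 0.3 | 4.6% | 4.4% | 273 |
| 0.4 | 8.3% | 8.2% | 295 |
| 0.5 | 13.4% | 13.2% | 331 |

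Break-even is at r² ≈ 1 − 1/1.0042 = 0.0042, that is r of about 0.06.

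**3. What this means for power.** For an illustrative difference of 0.36 residual SDs (an assumption) with 124 per arm, power is 0.81 without the covariate. With it, power is 0.81, 0.82, 0.84, 0.87 and 0.90 at r = 0.1, 0.2, 0.3, 0.4 and 0.5.

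**4. How r depends on what else is stable.** Take a score made up of fellow eye (weight w), study eye (weight 0.4, baseline to follow-up correlation 0.5), a stable non-visual trait (weight τ) and noise (SD 0.6 to 0.7), adjusted for baseline score and baseline study-eye BCVA. All these weights are assumptions. The CI narrows as follows, before the 0.2% correction.

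| | w = 0.3 | w = 0.7 |
|---|---|---|
| τ = 0 | 5.7-6.7% | 15.5-16.4% |
| τ = 0.5 | about 2% | about 7% |
| τ = 0.8 | about 1% | about 3% |

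With τ = 0.5 and w = 0.1 to 0.2 the gain is 0.3-1.1%. Once stable general health, mood or reporting style is allowed for, the baseline score does more of the work and the fellow eye adds less. A gain of 5% is therefore not a safe lower bound.

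**The case against.** The strongest reply is that nothing here is wrong. ANCOVA on the outcome's own baseline and the minimisation factors is valid and unbiased under randomisation, the protocol wording leaves room for judgement, and a detailed SAP is promised. That stands, and it is why this is a suggestion and not a correction. The covariate set is nevertheless stated in the protocol, so adding to it is a concrete change to a stated model.

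Stronger readings are tempting, and the document does not support them:

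- **That the intervals are certainly too wide.** A reader might infer this from the omission. It depends on r, which appears nowhere in the protocol, and the baseline score already absorbs part of the fellow-eye information. The gain may be close to nil.
- **That omitting the fellow eye biases the comparison.** Minimisation does not control fellow-eye vision, and with 124 per arm its arm difference has a standard error of √(2/124) = 0.127 SD. But chance imbalance is random error that the confidence interval already reflects, and the baseline score corrects for it in part.
- **That the EQ-5D-5L suffers equally.** None of its five dimensions is vision, so the argument is weaker there. Its use for QALYs is a separate bivariate regression of costs and QALYs under the health economic analysis plan, which the quoted sentence does not govern.

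It is also true that the primary outcome, the margin and the sample size are untouched.

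**Conclusion.** The point holds as a minor, nearly free improvement to the NEI VFQ-25 analysis. The stated model omits a pre-randomisation measure of the eye that was not operated on, although the outcome depends on both eyes and the value is already collected.

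The gain is between nothing and about 13% of CI width for r from 0.1 to 0.5, against a loss of about 0.2% if fellow-eye vision adds no information. The range rests on an assumed r and on 248 evaluable participants. The protocol offers no means of narrowing it, so no single figure should be claimed.

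**What to change.** Pre-specify baseline fellow-eye BCVA, as a continuous letter score, as an additional covariate in the NEI VFQ-25 model. Use the value from the baseline visit, which section 9.1 places before randomisation, and not a repeat measurement that section 12.4 may trigger before a delayed surgery. Name the covariate before any outcome data are seen, in the SAP or a protocol amendment, because a covariate chosen afterwards would not carry the same credibility.

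For the EQ-5D-5L group comparison the covariate is optional. The QALY regression and the primary analysis need no change.

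The cost is one degree of freedom, no new data and no change to the sample size.
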